6.14.3 Improvement in Daily ON-time, Responder Analysis

The number and percent of responders (at least 1h improvement in average daily ON-time) versus non-responders at Week 12 will be tabulated by treatment group.

Each dose level will be compared to placebo using a Cochran-Mantel-Haenszel (CMH) test. The risk difference for each dose level compared to placebo, corresponding 95% CI and p-value for the CMH statistic will be provided.

The following is the sample SAS code that will be used for this analysis:

```
PROC FREO DATA=DATAIN;
TABLES TRT01PN*RESP / RISKDIFF CMH;
ODS OUTPUT RISKDIFFCOL2 = RISK CMH = CMH PVAL;
RUN;
```

Where TRT01PN = Planned Treatment Group Number; RESP = Responder (0/1).

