5 RANDOMIZATION

At the baseline visit (Visit 1, Day 1) patients will be randomized 1:1:1:1 to receive one of three doses of mesdopetam (2.5 mg, 5 mg, or 7.5 mg) or placebo b.i.d. based on the randomization schedule prepared by the unblinded statistician.

During the first week (Day 1 evening dose to Day 9 morning dose) a run-in phase with either 5 mg mesdopetam or placebo b.i.d. will take place, during which all patients allocated to mesdopetam will receive 5 mg mesdopetam b.i.d. and patients allocated to placebo will receive placebo b.i.d. The purpose of the run-in period with 5 mg b.i.d. is to allow for a one-week dose titration for patients randomized to 7.5 mg b.i.d. In a previous Phase 2a study most patients tolerated 5 mg b.i.d. At Visit 2 (Day 9), patients will receive mesdopetam 2.5 mg, 5 mg or 7.5 mg or placebo b.i.d., as randomized.

Randomization will be performed via a web-based Interactive Response System (IRS), using a dynamic balancing (minimization) algorithm. Randomization will be stratified by average (based on at least two valid home diaries) of <6 daily hours and \geq 6 hours of daily ON-time with troublesome dyskinesia at baseline.

During the one-week run-in phase, the IRS will ensure all patients allocated to mesdopetam treatment will receive 5 mg mesdopetam b.i.d., followed by the randomized dose during the treatment period. Patients allocated to placebo will receive placebo during the first week run-in and then continue placebo during the whole treatment period. Any dose reduction will also be managed through the IRS to ensure that blinding is maintained.

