6.12.3 Primary Analysis

The number and percent of patients with valid diaries will be tabulated by treatment group and visit and a listing of diary completion will be provided. Descriptive statistics for the actual values by visit (including baseline) and change from baseline to each post-baseline visit (Visits 3, 4 and 5/EOT) in average daily ON-time without troublesome dyskinesia (hours) will be presented.

Change from baseline in average daily ON-time without troublesome dyskinesia (hours) will be analysed using a mixed model for repeated measures (MMRM) for all patients in the FAS. Change from baseline to Week 12 is the timepoint of interest for this analysis. Any missing data is assumed to be missing at random (MAR) for this analysis.

The model will include randomized treatment (2.5 mg, 5.0 mg, 7.5 mg, or placebo b.i.d.), visit, country, and treatment by visit interaction as explanatory, fixed effect variables. Country will be

Worldwide Clinical Trials Controlled Quality Management Document		
WORLDWIDE CLINICAL TRIALS	Sponsor:	Integrative Research Laboratories Sweden AB
	Protocol Number:	IRL790C005
STATISTICAL ANALYSIS PLAN. PHASE 2-3-4		

weighted by the number of patients participating from each county. Baseline value for average daily hours of ON time without troublesome dyskinesia will be included as a continuous covariate along with the randomisation stratification factor of daily hours spent in ON-time with troublesome dyskinesia (<6 hours, \geq 6 hours).

An unstructured covariance matrix will be assumed for within-patient correlation over time. If the model fails to converge, the first approach for which the model converges among the following will be used: banded Toeplitz (TOEP), compound symmetry (CS) and variance component (VC).

The LS mean estimate, corresponding SE, and 95% CI for the change from baseline at each postbaseline visit will be obtained from the model and presented for each treatment group. The estimated treatment difference for each dose level compared to placebo and the combined dose levels compared to placebo, the corresponding SE, and p-value will also be presented by visit.

A line plot showing the LS mean ($\pm 95\%$ CI) change from baseline at each visit for each treatment group will also be provided.

The following is the sample SAS code that will be used for this analysis:

```
PROC MIXED DATA= analysis (where = (avisitn ne 0));
    ODS OUTPUT LSMeans=LSMeans Diffs=Diffs LSMEstimates=Estimates;

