6.12.5.2 ANCOVA Analysis

An analysis of covariance (ANCOVA) will also be performed using the FAS. The ANCOVA model will be adjusted for the following covariates: randomized treatment, baseline value for average daily hours of ON time without troublesome dyskinesia (continuous covariate), as well as randomisation stratification factor for daily hours spent in ON-time with troublesome dyskinesia (<6 hours, \geq 6 hours). The dependent variable is the change from baseline in average daily ON-time (hours) at Week 12. Missing observations will not be imputed.

The LS means, SEs, and 95% CIs will be provided for each treatment group, as well as treatment difference estimates, SEs, and p-values for each dose level and combined dose groups compared to placebo.

The following is the sample SAS code that will be used to implement this analysis:

```
PROC MIXED DATA= DATAIN;
CLASS TRT01PN STRATF;
MODEL CHG_WEEK12 = TRT01PN BASE STRATF / SOLUTION;
LSMEANS TRT01PN / CL DIFF OM;
LSESTIMATE TRT01PN "Difference at Week 12" 1 1 1 -3 / CL e OM;
LSESTIMATE TRT01PN "Combined at Week 12" 1 1 1 0 / CL e OM;
RUN;
```

Where TRT01PN = Planned Treatment Group Number; BASE = Baseline Value; CHG_WEEK12 = Change from Baseline at Week 12; STRATF = Stratification Factor.

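### The sample code for the responder analysis (SAP 6.14.3) does not deliver the dose-versus-placebo results its own text specifies, and it leaves out the randomisation stratum

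*SAP*

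**What the plan says.** The text of SAP 6.14.3 sets out pairwise comparisons: "Each dose level will be compared to placebo using a Cochran-Mantel-Haenszel (CMH) test". It also fixes the outputs: "The risk difference for each dose level compared to placebo, corresponding 95% CI and p-value for the CMH statistic will be provided". It names no stratification variable.

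The code beneath it, introduced as a sample that is to be used for this analysis, is one PROC FREQ call with the statement "TABLES TRT01PN*RESP / RISKDIFF CMH". Its variables are defined as "Where TRT01PN = Planned Treatment Group Number; RESP = Responder (0/1". No statement restricts the data to one dose plus placebo.

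Three other places bear on this:

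- SAP 5 has four arms: "patients will be randomized 1:1:1:1 to receive one of three doses of mesdopetam (2.5 mg, 5 mg, or 7.5 mg) or placebo b.i.d". It also fixes the balancing factor: "Randomization will be stratified by average (based on at least two valid home diaries"), cut at 6 hours of ON-time with troublesome dyskinesia.
- The primary MMRM (SAP 6.12.3) includes it, "along with the randomisation stratification factor of daily hours spent in ON-time with" troublesome dyskinesia. So does the supportive ANCOVA (SAP 6.12.5.2): "as well as randomisation stratification factor for daily hours spent in ON-time with troublesome dyskinesia".
- SAP 6.13.3.3 and the opening of SAP 6.14 require the pooled active doses to be compared with placebo in the exploratory analyses too. SAP 6.14.3 mentions only the individual doses.

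**The concern.** Text and code in the same section describe different analyses. The text asks for three comparisons of two arms; the code builds one table of four arms. A programmer who follows the code gets p-values for other questions and cannot fill the risk-difference cells. A programmer who follows the text has to devise the split, and has to decide without guidance whether to stratify.

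The missing stratum is a second gap. CMH is a method for combining tables across strata. With no stratum it reduces to the Pearson chi-square multiplied by (N−1)/N, so naming CMH without a stratum leaves the method half specified. The response variable is a dichotomy of the same diary measure that the MMRM and ANCOVA adjust for this factor.

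This is the SAP's only analysis counting patients who reach the 1-hour gain that protocol 11.2.3.1 treats as clinically meaningful, so it is likely to be cited when the primary result is interpreted. Settling the method before unblinding avoids a later choice between two p-values.

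**Working it through.** **The plan's own figure.** SAP 6.14.3 states no number to reproduce. The 92% power in SAP 4 concerns the primary endpoint; it reproduces (31 per group, difference 3 h, SD 3.5 h: normal approximation 0.921) and plays no part here.

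**Step 1: what the printed table can give.** TRT01PN has 4 levels and RESP has 2. A 4x2 table has (4−1)(2−1) = 3 degrees of freedom for general association, plus a 1-df correlation statistic on row scores. Neither contrasts one dose with placebo. A risk difference needs two rows, and the PROC FREQ option applies to 2x2 tables (a property of the software, not stated in the documents).

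**Step 2: an assumed example.** The documents give no responder rates. Take N = 154 (the increased size in SAP 4) and responders 15/38, 18/38, 23/39 and 12/39 for 2.5, 5, 7.5 mg and placebo.

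*7.5 mg against placebo, which the text asks for.*
- Risk difference = 23/39 − 12/39 = 0.590 − 0.308 = 0.282.
- Responders in the pair: 35 of 78. Expected on 7.5 mg = 39 × 35/78 = 17.5.
- Variance = 39 × 39 × 35 × 43 / (78² × 77) = 4.886.
- CMH = (23 − 17.5)² / 4.886 = 6.19 on 1 df, p = 0.013.

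*All four arms, as the code prints.*
- Responders 68 of 154; expected 16.78, 16.78, 17.22, 17.22.
- Pearson = [Σ(O−E)²/E] / (86/154) = 3.800 / 0.5584 = 6.804. Times 153/154 gives 6.760 on 3 df, p = 0.080.
- Correlation, scores 1 to 4 with placebo last: Σ score × (O−E) = −2.883. Variance = 68 × 86 × (154 × 1165 − 387²) / (154² × 153) = 47.77. Statistic = 8.312 / 47.77 = 0.174 on 1 df, p = 0.68.

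The correlation statistic is near zero because placebo is scored above 7.5 mg. That coding is inferred from the coefficient order in SAP 6.12.3 and 6.12.5.2; SAP 6.14.3 does not state it.

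**Step 3: the cost of leaving out the stratum.** Simulated power of one dose against placebo at two-sided 0.05, 38 per arm, 19 per stratum per arm. The rates and the even, balanced split are assumptions.

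| Placebo, stratum 1/2 | Active, stratum 1/2 | Unstratified | Stratified |
|---|---|---|---|
| 35% / 35% | 65% / 65% | 76% | 76% |
| 25% / 40% | 55% / 70% | 76.1% | 76.3% |
| 20% / 50% | 50% / 80% | 76% | 79% |
| 15% / 45% | 40% / 80% | 78% | 82% |
| 10% / 50% | 35% / 85% | 79% | 86% |
| 10% / 60% | 40% / 90% | 80% | 89% |

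With both arms at the placebo rates, unstratified type I error was 0.054 (35%/35%), 0.043 (20%/50%) and 0.022 (10%/60%). The stratified test gave 0.052, 0.053 and 0.048. Leaving out the stratum therefore makes the test conservative when the stratum is prognostic; it does not inflate error.

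**The case against.** The strongest reply is that the plan is right and only an illustrative snippet falls short. The text names the correct comparisons and outputs, the code is labelled a sample, and an input dataset already cut to one dose plus placebo would make the same line a 2x2 table. SAP 6.3.3 requires independent programming by a statistician for all statistical analyses, so an empty risk-difference column would be noticed. This largely stands. A reader might infer that the SAP has chosen the wrong responder comparison, or that the wrong p-value would end up in the report; the documents support neither. What remains is that no filtering step is written, and filtering would not supply a stratum.

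A second reply is that no document promises a stratified responder test, that an unstratified test on a 2x2 table is valid, and that the neighbouring MMSE ANCOVA (SAP 6.14.2) also omits the factor. The first two points are correct; the third concerns a different variable. Stratifying is thus a matter of consistency with the other analyses of this diary variable and not the repair of a broken commitment.

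A reader might also infer that the unstratified test necessarily loses power. It does not: a 15-point gap between strata costs 0.2 points. Nor does the stratum alone limit what a patient can gain, since good ON-time can also come from OFF-time, which protocol 11.2.3.1 likewise counts as bad time.

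**Conclusion.** The point holds as a conflict between text and code plus an incomplete method. As printed, the call gives no dose-versus-placebo p-value and no risk difference. This follows from the table's dimensions and needs no assumption about rates; the example's p-values only illustrate it.

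The benefit of stratifying is conditional. It is nil if the stratum is not prognostic. It is about 4 to 7 points in the scenarios with 30- and 40-point gaps in placebo response where the effect differs between strata, and about 2 points for a 30-point gap with a constant effect. These figures rest on assumed rates and an even split between strata.

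The stakes are limited. The analysis is exploratory, was added in SAP 9 (item 8), lies outside the testing hierarchy of SAP 6.15 and did not drive the sample size. A reader might infer that the trial's main findings are at risk; the primary and key secondary conclusions are unaffected. It is still worth correcting before unblinding.

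**What to change.** In SAP 6.14.3:

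1. For each dose, restrict the data to that dose plus placebo and run `TABLES STRATF*TRT01PN*RESP / CMH RISKDIFF(COMMON)`, with the risk difference taken for the responder column, as the present code intends.
2. Add the pooled comparison required by SAP 6.13.3.3 and 6.14: all active doses against placebo, with a two-level active/placebo variable in place of TRT01PN.
3. For each comparison report the stratified CMH p-value and the Mantel-Haenszel common risk difference with its 95% CI.
4. State that the stratum is the randomisation factor used in the primary model. This matters because SAP 6.12.4.3 also refers to a modified stratification factor without defining it there.

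The cost is a sentence or two and a few lines of code. No data, visits or patients are involved, and in the simulated case with no stratum effect the stratified test lost no power.

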6.14.4 MDS-UPDRS: Part 1, and Part 4 Total Scores

MDS-UPDRS Part 1 total score, and Part 4 total score will be summarized separately by treatment group and visit. Change from baseline for each part total score will be summarised, analysed, and reported (including model estimates and line plot) in the same manner as for the primary analysis, as described in Section 6.12.3.

QMD Ref: Worldwide-TMP-ST-005-7.0 Effective: 12Aug2019	Governing QMD: Worldwide-SOP-ST-001	
Confidentiality Statement		
This document is the property of Worldwide Clinical Trials Inc. and may not be duplicated, copied, altered or removed from company without prior approval from Worldwide Quality Assurance or in compliance with Worldwide Standard Operating Procedures.		
REF: Worldwide-TMP-QA-001f-1.3 Page		

6.14.5 Freezing and Freezing of Gait, MDS-UPDRS: Question 2.13 + Question 3.11

MDS-UPDRS Question 2.13 +Question 3.11 sum score and change from baseline by visit will be provided by treatment group. Change from baseline in question 2.13 + question 3.11 sum score will be analysed and reported (including model estimates and line plot) in the same manner as for the primary analysis, as described in Section 6.12.3.

6.15 Multiplicity

Multiple dose levels have been included in the study design to evaluate the dose-response relationship of mesdopetam with the hypothesis that the 7.5 mg b.i.d. dose will be the most efficacious of the dose levels studied.

Two key secondary endpoints (change from baseline in ON-phase dyskinesia assessed by MDS-UPDRS Question 4.2 and change from baseline in disability associated with ON-phase dyskinesia assessed with the sum score of UDysRS parts 1b and 4) will also be evaluated and thus a strategy for controlling the overall error rate whilst maintaining the planned study power is required.

To such aim, a hierarchical testing strategy will be used whereby first the 7.5 mg b.i.d. will be tested at a 5% level on the primary endpoint, and should the test be significant, the 2 key secondary endpoints will be tested for the 7.5 mg b.i.d. dose using a truncated Hochberg procedure with a truncation parameter $\gamma = 0.7$. This procedure works as follows for n = 2 tests:

- 1) p-values are sorted in ascending order as p_1 and $p_{2;}$
- 2) The largest p-value, p₂, is compared against the modified critical value c₂ below:

$$c_2 = \left[\frac{\gamma}{n-i+1} + \frac{1-\gamma}{n}\right]\alpha = \left[\gamma + \frac{1-\gamma}{2}\right]\alpha = \left[0.7 + \frac{0.3}{2}\right]0.05 = 0.0425$$

(where n = 2 and i = 2)

- 3) If $p_2 \le c_2$ then all key secondary hypotheses are rejected, otherwise the hypothesis associated with p_2 is retained and the other p-value, p_1 , is compared against the critical value c_1 , which can be obtained from the formula in 2) by replacing *i* with 1, leading to a critical value of 0.025;
- 4) If $p_1 \le c_1$ then the associated hypothesis is rejected, otherwise all hypotheses are retained and no more testing of primary or key secondary hypotheses for the lower doses is performed.

QMD Ref: Worldwide-TMP-ST-005-7.0 Effective: 12Aug2019	Governing QMD: Worldwide-SOP-ST-001		
Confidentiality Statement			
This document is the property of Worldwide Clinical Trials Inc. and may not be duplicated, copied, altered or removed from company without prior approval from Worldwide Quality Assurance or in compliance with Worldwide Standard Operating Procedures.			
phot approval nonit wondwide Quanty Assurance of in compnance with wondwide Standard Operating Proceedings.			
REF Worldwide-TMP-OA-001f-1 3	Page 40 of 49		

Worldwide Clinical Trials Controlled Quality Management Document		
	Sponsor:	Integrative Research Laboratories Sweden AB
CLINICAL TRIALS	Protocol Number:	IRL790C005
STATISTICAL ANALYSIS PLAN. PHASE 2-3-4		

If at least one hypothesis is rejected in the above steps, then the primary endpoint is tested for the 5 mg b.i.d. dose at an alpha level that depends on how many hypotheses were rejected in the truncated Hochberg procedure and the truncation parameter γ .

To derive the amount of alpha level to carry over to the next level of testing, we account for how many hypotheses were rejected:

- a) If all or none were rejected, then we carry over, respectively, 0.05 (full α) or 0 (no α);
- b) If only one hypothesis were rejected, the amount of alpha to carry forward is given by:

$$((1-\gamma)|I|\alpha)/n = ((1-0.7)|1|0.05)/2 = 0.0075$$

Testing of the primary endpoint for the 5 mg b.i.d. dose is then conducted at the specified alphalevel and then, depending on the significance of this test, another truncated Hochberg procedure with the same truncation parameter is conducted for the key secondary endpoints, using the same alpha level carried over to test for the primary endpoint at 5 mg b.i.d. to derive the critical values for the testing using the same formulas shown above.

Once the truncated procedure has been conducted, the same approach to derive the amount of alpha that can be carried forward to the testing of the primary endpoint for the lower dose is then followed. Once this testing is complete, if the primary endpoint is significant at the pre-specified alpha level, the key secondary endpoints are tested using a standard Hochberg procedure, which is conducted similarly to its truncated version but with c_1 and c_2 being equal to $\alpha/2$ and α , respectively (where α is the significance level at which the primary endpoint was tested for the 2.5 mg b.i.d. dose).

An ordered tabulation of the endpoints tested, p-values observed, alpha-level tested against and acceptance or otherwise of the null hypothesis at each stage will be presented.

6.16 Pharmacokinetic Analyses

Plasma concentrations of mesdopetam and its two main metabolites (IRL902 [N-dealkylated] and IRL872 [acetylated]) will be obtained pre-dose and 2 hours post-dose (as an estimate of C_{max}) at Visit 4 (Week 8) and Visit 5 (Week 12).

QMD Ref: Worldwide-TMP-ST-005-7.0 Effective: 12Aug2019	Governing QMD: Worldwide-SOP-ST-001	
Confidentiality Statement		
This document is the property of Worldwide Clinical Trials Inc. and may not be duplicated, copied, altered or removed from company without prior approval from Worldwide Quality Assurance or in compliance with Worldwide Standard Operating Procedures.		
REF: Worldwide-TMP-QA-001f-1.3 Page 2		

Worldwide Clinical Trials Controlled Quality Management Document		
WORLDWIDE CLINICAL TRIALS	Sponsor:	Integrative Research Laboratories Sweden AB
	Protocol Number:	IRL790C005
STATISTICAL ANALYSIS PLAN. PHASE 2-3-4		

Concentration data will be summarized by analyte, adjusted dose level, and visit at each scheduled sample time (nominal time) for the PK analysis set, using descriptive statistics. Line plots will also be provided showing mean (SD) by dose level and visit for each analyte.

In addition, concentration data will be summarized by genotype (poor, intermediate, normal, and ultrarapid metabolizer), adjusted dose level, and visit at each scheduled sample time (nominal time) using descriptive statistics and line plots for the CYP Genotype Subset.

All concentration data will be listed.

